### **12.3. Demographics and Baseline Characteristics**

For De Novo Subjects, baseline is defined as Visit 2. For Rollover Subjects, baseline is defined as the baseline visit in the antecedent study.

Summary statistics will be provided for all demographic variables and baseline characteristics. Medical history will be summarized for the safety population using the number of observations and percentage of subjects reporting each category.

### **12.4. Methods of Analysis for Efficacy Endpoints**

Efficacy analyses of treatment effect over time will be based on data from the FAS population.

All endpoints listed below will be summarized by study timepoint and by change from baseline using descriptive statistics as appropriate.

CONFIDENTIAL

The information contained herein may not be used, disclosed, or published without the written consent of Biogen MA Inc.

[REDACTED]

[REDACTED]

[REDACTED]

[REDACTED]

[REDACTED]

[REDACTED]

#### Clinical endpoints

- ARR
- Proportion of subjects experiencing a relapse
- EDSS score
- T25-FW score
- Proportion of subjects with No Evidence of Disease Activity (NEDA) at Week 96

#### Other endpoints

- SF-12 (domain score)
- EQ-5D-5L VAS scores

The ARR will be summarized as number of relapses per subject per year, in which subject study duration is calculated as the time from first dose to last dose of study medication +1. NEDA will indicate an absence of select clinical (MS relapse and disease progression) [REDACTED] outcomes.

### **12.5. Methods of Analysis for Pharmacokinetic Endpoints**

PK analyses will be performed using the PK population. Individual plasma concentrations will be listed by actual sampling times and summarized by nominal sampling times using descriptive statistics. Plots of individual and mean concentrations over time will also be generated. PK parameters will be calculated using noncompartmental analysis. Parameters will be estimated using actual elapsed time from dosing and summarized using descriptive statistics. A subject listing of individual PK parameters will be provided.

Additionally, PK concentration data obtained from this study will may be combined with data from other studies to develop a population PK model, which will be reported separately.

CONFIDENTIAL

The information contained herein may not be used, disclosed, or published without the written consent of Biogen MA Inc.

## **12.6. Methods of Analysis for Safety Endpoints**

The safety analysis will be carried out using the safety population. Reported AE terms will be coded using the Medical Dictionary for Regulatory Activities.

Safety assessments will be summarized using descriptive statistics along with supportive listings. The number and percentage of TEAEs will be summarized by system organ class, and preferred terms within each system organ class. SAEs and AEs resulting in treatment discontinuation will be summarized.

Observed values and change from baseline in laboratory parameters, vital signs, ECG parameters, and scores on the C-SSRS will be summarized by study visit. The number and percentage of subjects who have met potentially clinically significant criteria at any postbaseline visit will be summarized.

Listings will be provided for all safety endpoints.

## **12.7. Interim Analyses**

Not applicable.

## **12.8. Sample Size Considerations**

No formal sample size calculation is performed for this study. A sample size of approximately 1000 subjects will contribute to the long-term safety experience of ALKS 8700 in subjects with RRMS, taking into account International Council for Harmonisation (ICH) guidance on the extent of patient exposures required to assess clinical safety for a new drug.

CONFIDENTIAL

The information contained herein may not be used, disclosed, or published without the written consent of  
Biogen MA Inc.

## **13. ETHICAL AND REGULATORY REQUIREMENTS**

The Sponsor, any contracted third party, and the Investigator must comply with all instructions, regulations, and agreements in this protocol and applicable ICH and GCP guidelines and conduct the study according to local regulations.

The Investigators are responsible for demonstrating timely oversight of all clinical trial data from their site, including data external to the electronic data capture system, such as laboratory, imaging, and electronic clinical outcomes assessment data. Investigators must approve all their data on completed eCRFs by signing electronically, at the subject, visit, or casebook level, at any time prior to an interim lock or database lock, as well as before any subsequent re-lock. The electronic data capture system does not prohibit Investigator approval or signing in any way.

The Investigator may delegate responsibilities for study-related tasks where appropriate to individuals sufficiently qualified by education, training, and experience, in accordance with applicable ICH and GCP guidelines. The Investigator should maintain a list of the appropriately qualified persons to whom significant study-related duties have been delegated. The Investigator is responsible for supervising those individuals and for implementing procedures to ensure the integrity of the tasks performed and any data generated.

### **13.1. Declaration of Helsinki**

This study will be performed in alignment with the ethical principles outlined in the Declaration of Helsinki.

### **13.2. Ethics Committee**

If the Investigator makes any changes to the ICF, the Sponsor must approve the changes before the ICF is submitted to the ethics committee. A copy of the approved ICF must be provided to the Sponsor. After approval, the ICF must not be altered without the agreement of the relevant ethics committee and the Sponsor.

It is the responsibility of the Investigators to ensure that all aspects of institutional review are conducted in accordance with current applicable regulations.

The Sponsor must receive a letter documenting ethics committee approval, which specifically identifies the protocol, protocol number, and ICF, prior to the initiation of the study. Protocol amendments will be subject to the same requirements as the original protocol.

Initial ethics committee approval as well as all materials approved by the ethics committee for this study, including the subject consent form and recruitment materials, must be maintained by the Investigator and made available for inspection.

CONFIDENTIAL

The information contained herein may not be used, disclosed, or published without the written consent of Biogen MA Inc.

A progress report must be submitted to the ethics committee at required intervals and not less than annually.

At the completion or termination of the study, where required, the study site must submit a close-out letter to the ethics committee and the Sponsor.

### **13.3. Changes to Final Protocol**

All protocol amendments must be submitted to the ethics committee and regulatory authorities if required by local law. Protocol modifications that affect subject safety, the scope of the investigation, or the scientific quality of the study must be approved by the ethics committee before implementation of such modifications to the conduct of the study. If required by local law, such modifications must also be approved by the appropriate regulatory agency prior to implementation.

However, the Sponsor may, at any time, amend this protocol to eliminate an apparent immediate hazard to a subject. In this case, the appropriate regulatory authorities will be notified subsequent to the modification.

In the event of a protocol modification, the ICF may require similar modifications (see Section 13.4).

### **13.4. Informed Consent**

Prior to performing any study-related activities under this protocol, including screening tests and assessments, informed consent with the approved ICF must be obtained.

A copy of the signed and dated ICF and assent must be given to the subject and/or the subject's legally authorized representative. The original signed and dated ICF will be retained with the study records. Local regulations must be complied with in respect to the final disposition of the original and copies of the signed and dated ICFs.

Confirmation of informed consent and assent must also be documented in the subject's medical record.

When additional information that may affect subjects' willingness to continue in the study becomes available, the Investigators will be notified in a timely manner, according to all local and applicable law. An updated ICF may be required.

### **13.5. Confirmation of Willingness to Continue in the Study**

Written documentation of a subject's willingness to continue participation in the study will be required if one or more of the following occurs during the study:

- MS relapse
- Disability progression (based on EDSS)

CONFIDENTIAL

The information contained herein may not be used, disclosed, or published without the written consent of Biogen MA Inc.

If any of the above events occur, the Investigator will use clinical judgment as to whether or not the subject should continue participation in the study. In addition, the Investigator will discuss the event(s) with the subject and ensure that the subject is given full information regarding the potential and possible risks and benefits of continuing participation in the study. Each subject will receive an institutional review board (IRB)/ ethics committee-approved form that summarizes the pertinent information and will be given ample time to read the form and ask questions.

All information is to be provided in a language understandable to the subject and must not include any language that waives the subject's legal rights. Subjects must also be informed of their right to refuse continued participation in the study without prejudice at any time during the study. If the subject chooses to continue participation in the study, he/she must sign the form indicating his/her willingness to continue before any further study-specific procedures are conducted.

The time of written confirmation of willingness to continue in the study must be documented. The Investigator must maintain the original signed form in the subject's source documents. A copy of the signed form must be given to the subject.

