### 7.2.1.      **Rescue**

Subjects will be eligible to remain on assigned study treatment for 96 weeks, even if they experience a relapse (see Section 7.2.2). In the event of a confirmed acute event (relapse), the treating neurologist may opt to prescribe 1000 mg of oral or IV methylprednisolone treatment (administered once daily or in divided doses) for 3-5 days with no taper. Treatment with oral or IV methylprednisolone will not affect the subject's eligibility to continue in the study. The subject will continue on study treatment while being treated with methylprednisolone. Subjects may also refuse relapse treatment. Any deviations from this recommended treatment must first be discussed with the Medical Monitor.

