### **9.1.2. Structured Interviews and Questionnaires**

#### **9.1.2.1. Expanded Disability Status Scale**

The EDSS [Kurtzke 1983] is used to measure and evaluate MS patients' level of functioning. The EDSS provides a total score on a scale that ranges from 0 to 10. The first levels 1.0 to 4.5 refer to people with a high degree of ambulatory ability and the subsequent levels 5.0 to 9.5 refer to the loss of ambulatory ability. The range of main categories include (0) = *normal neurologic examination*; to (5) = *ambulatory without aid or rest for 200 meters*; *disability severe enough to impair full daily activities*; to (10) = *death due to MS*. In addition, it also provides 8 subscale measurements called FS scores: pyramidal (motor function); cerebellar; brainstem, sensory; bowel and bladder; visual, cerebral or mental; and other. FS are scored on a scale of 0 (low level of problems) to 5 (high level of problems) to best reflect the level of disability observed clinically. The total EDSS score is determined by 2 factors: gait and FS scores. Expanded disability status scale scores below 4.0 are determined by the FS scores alone. Expanded disability status scale scores between 4.0 and 9.5 are determined by both gait abilities and FS scores. For this study, the fatigue score should be recorded but not included in the calculation of the cerebral FS score.

The Investigator or designee will complete the EDSS according to the schedule in [Table 1](#). A sample of the EDSS will be provided to the study sites outside of this protocol.

Progression of disability that is sustained for 12 weeks is defined by one of the following: an EDSS increase of at least 1.5 points from baseline EDSS = 0, an EDSS increase of at least a 1.0 point from baseline EDSS between 1.0 and 5.5 (inclusive), or an EDSS increase of at least 0.5 points from baseline EDSS = 6.0.

If a subject experiences progression of disability as defined above, the subject must be informed of this progression. If the Investigator determines the subject may continue participation and the subject is willing, subjects will also be required to provide written confirmation of their willingness to continue participation in the study as described in [Section 13.5](#). Subjects who prematurely discontinues either the study or study treatment will complete an ET visit and all safety follow-up assessments as described in [Section 8](#).

CONFIDENTIAL

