### **12.1. General Considerations**

The statistical analysis methods are described below. Additional details will be provided in the Statistical Analysis Plan.

In general, summary statistics (number of subjects, mean, standard deviation, median, minimum, and maximum values for continuous variables, and number and percentage of subjects in each category for categorical variables) will be provided for all parameters. All statistical results will be presented based on observed values. All individual subject level data will be presented as data listings.

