3.5.3. Clinical endpoints

- The change from baseline in the EDSS score
- Proportion of subjects experiencing a relapse at Week 96
- Annualized Relapse Rate (ARR) at Week 96
- Time to onset of 12-week confirmed disability progression
- Change in 25-Foot Walk from Baseline
- Proportion of subjects with No Evidence of Disease Activity (NEDA) at Week 96

EDSS Score

The EDSS is used to measure and evaluate MS patients' level of functioning. The EDSS provides a total score on a scale that ranges from 0 to 10. The first levels 1.0 to 4.5 refer to people with a high degree of ambulatory ability and the subsequent levels 5.0 to 9.5 refer to the loss of ambulatory ability. The range of main categories include (0) = normal neurologic exam; to (5) = ambulatory without aid or rest for 200 meters; disability severe enough to impair full daily activities; to (10) = death due to MS. In addition, it also provides eight subscale measurements called Functional System (FS) scores: pyramidal (motor function); cerebellar; brainstem, sensory; bowel and bladder; visual, cerebral or mental; and other. The Functional Systems (FS) are scored on a scale of 0 (low level of problems) to 5 (high level of problems) to best reflect the level of disability observed clinically. The total EDSS score is determined by two factors- gait and FS scores. EDSS scores below 4.0 are determined by the FS scores alone. EDSS scores between 4.0 and 9.5 are determined by both gait abilities and FS scores. For this study, the fatigue score should be recorded but not included in the calculation of the cerebral FS score.

The EDSS score and change from baseline during the Treatment Period will be summarized by enrollment group and overall.

Relapse

A protocol-defined relapse consists of the following:

- New or recurrent neurologic symptoms, not associated with fever or infection, lasting for at least 24 hours, accompanied by one or more of the following:
 - New objective neurological findings upon examination by the treating neurologist that are functionally consistent with findings on the EDSS (performed within

7 days of onset of symptoms) with an increase over the prior visit of ≥ 0.5 for the total score,

- An increase of ≥ 2 in one FS subscale scores and/or
- An increase of ≥ 1 in two FS subscale scores, except bladder/cognitive changes.

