3.5.4. Patient Reported Outcomes

The following patient reported outcomes will be summarized for each enrollment group and overall:

- The change from baseline in the Short Form 12 Health Survey (SF-12) component and summary scores through Week 96
- The changes from baseline in the EQ-5D-5L visual analog scale (VAS) scores through Week 96

Short Form 12 Health Survey (SF-12) Component Scores

Quality of life will be assessed using the 12-item Short-Form health survey Version 2 (SF 12v2) [3]. The 12-item Short Form or SF-12 is a generic quality of life (QOL) measure based on the SF-36 Health Survey. The SF-12 captures approximately 90% of the variance of the SF 36. The SF-12 provides two summary indices of health-related quality of life: the Physical Component Summary (SF-12 PCS) and the Mental Component Summary (SF-12 MCS). SF-12 PCS and SF12 MCS scores will be computed using the transformed scores of 12 questions and range from 0 to 100 (Mean=50, standard deviation [SD] =10 in the general US population), where zero indicates the lowest level of health measured by the scales and 100 indicates the highest level of health [3].

EQ-5D-5L Visual Analog Scale (VAS) Scores

The 5-level EQ-5D version (EQ-5D-5L) [4] is designed for self-completion by subjects and consists of 2 pages - the EQ-5D-5L descriptive system and the EQ visual analog scale (VAS). The EQ-5D-5L descriptive system comprises the following 5 dimensions: mobility, self-care, usual activities, pain/discomfort, and anxiety/depression. Each dimension has 5 levels: no problems, slight problems, moderate problems, severe problems, and extreme problems. The EQ VAS records the respondent's self-rated health on a vertical, visual analog scale where the anchors are labeled 'Best imaginable health state' (score of 100) and 'Worst imaginable health state' (score of 0). The EQ-5D-5L descriptive system can be converted into a single summary EQ-5D Index [5].

The Patient Reported Outcomes scores and changes from baseline during the Treatment Period will be summarized by enrollment group and overall.

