7. GENERAL STATISTICAL METHODOLOGY

In general, summary statistics (n, mean, SD, median, minimum, and maximum for continuous variables, and number and percentage of subjects in each category for categorical variables) will be provided by treatment group. All summary tables will be based on observed data, and missing values will not be imputed unless otherwise indicated. Measurements collected from unscheduled visits or repeated assessments will not be included in the by-visit summary tables or figures, but will be included in the derivation of the last post-baseline value during treatment, the analyses for the potentially clinically significant (PCS) post-baseline values, and subject listings. Source data for the summary tables and statistical analyses will be presented as subject data listings.

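### By-visit EDSS and quality-of-life means can look too favourable if subjects who worsen leave more often, and the SAP does not say where early-termination scores are summarized

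*Protocol*

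**What the plan says.** **Decision point.** Under Protocol 13.5, once a relapse or EDSS progression occurs, "the Investigator will use clinical judgment as to whether or not the subject should continue participation in the study". A subject who stays must sign a form before any further study procedure. Protocol 9.1.2.1 repeats the condition for progression: "If the Investigator determines the subject may continue participation and the subject is willing". Lack of efficacy is a listed withdrawal reason in Protocol 8.3. For relapse, Protocol 7.2.1 also states: "Subjects will be eligible to remain on assigned study treatment for 96 weeks, even if they experience a relapse".

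**Data after exit.** Protocol 8.1 and 8.3 ask subjects who stop early to attend an ET visit, with the Visit 15 assessments, and a safety visit two weeks later. SAP Table 1 schedules EDSS, SF-12 and EQ-5D up to Visit 15/ET and not at Visit 16.

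**Analysis.** Protocol 12.1: "All statistical results will be presented based on observed values". Protocol 12.4: "All endpoints listed below will be summarized by study timepoint and by change from baseline using descriptive statistics as appropriate". SAP 7: "All summary tables will be based on observed data, and missing values will not be imputed unless otherwise indicated". SAP 3.5.3: "The EDSS score and change from baseline during the Treatment Period will be summarized by enrollment group and overall". SAP 3.5.4: "The Patient Reported Outcomes scores and changes from baseline during the Treatment Period will be summarized by enrollment group and overall". SAP 7 mentions a last post-baseline value, but 3.5.3 and 3.5.4 make no use of it.

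**Visit assignment.** SAP 6.1 takes the nominal eCRF visit as the analysis visit unless the dataset specification, a separate document, says otherwise. It leaves unscheduled visits out of by-visit statistics. Visit 15 and ET share one column in both schedules.

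**The concern.** Treatment effect over time is one of the study's two objectives, and a table of mean change by visit is its natural display. If subjects who relapse or progress leave more often than others, each later row describes a more selected group. A flat EDSS or quality-of-life curve could then reflect who remained, not how subjects fared. With no control arm, the table itself cannot separate the two explanations.

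The planned outputs do not link exit to the event. Disposition is tabulated by eCRF reason (SAP 3.1.2), and a subject who declines to re-sign after a relapse could be recorded as a withdrawal by the subject or a physician decision. The EDSS taken at an unscheduled relapse visit is not in the by-visit means. The ET score, often the last one available, has no stated row.

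**Working it through.** The plan gives no figure to reproduce: no withdrawal rate, event rate, standard deviation or sample-size calculation (Protocol 12.8). All rates below are assumptions.

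**Step 1: direction, from a two-group mixture.** Let p be the share of subjects who worsen, w the withdrawal among them, d the withdrawal among the rest, and D the difference in mean change between the groups. Among those still observed, the worsened share is s = p(1−w) / [p(1−w) + (1−p)(1−d)], and the bias of the row mean is (s−p)·D. For EDSS take D = 1.0, the smallest progression step for baseline 1.0 to 5.5 (Protocol 9.1.2.1). With p = 10%:

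- w = d = 15%: s = 0.085/0.85 = 0.100, bias 0.
- w = 25%, d = 15%: s = 0.075/0.840 = 0.089, bias −0.011.
- w = 40%, d = 15%: s = 0.060/0.825 = 0.073, bias −0.027.
- w = 60%, d = 15%: s = 0.040/0.805 = 0.050, bias −0.050.
- w = 10%, d = 20%: s = 0.090/0.810 = 0.111, bias +0.011 (reversed).

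Over p = 5% to 20% and w = 25% to 60%, with d = 15%, the EDSS bias runs from −0.006 to −0.095. With an assumed 8-point VAS loss in worsened subjects, the EQ-5D VAS bias on the same grid is +0.05 to +0.76 points.

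**Step 2: size over repeated visits, by simulation.** 400,000 subjects; baseline EDSS about 2.7; 10% or 20% worsening at a mean of 0.9 points per year; visit noise SD 0.35; scores rounded to 0.5; protocol thresholds met at two consecutive 12-weekly visits. This gives 8.5% or 16.6% confirmed progression by Week 96. Background drop-out is 3% per 12 weeks. Mean EDSS change at Week 84:

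| Worsening | Exit at confirmation | Nobody leaves | Observed (shortfall) | Repeated-measures likelihood (shortfall) |
|---|---|---|---|---|
| 10% | 20% | 0.149 | 0.128 (0.021, 14%) | 0.140 (0.009, 6%) |
| 10% | 40% | 0.148 | 0.106 (0.042, 28%) | 0.128 (0.020, 14%) |
| 10% | 60% | 0.148 | 0.085 (0.063, 43%) | 0.114 (0.034, 23%) |
| 20% | 20% | 0.294 | 0.256 (0.038, 13%) | 0.284 (0.010, 3%) |
| 20% | 40% | 0.294 | 0.216 (0.078, 27%) | 0.270 (0.024, 8%) |
| 20% | 60% | 0.295 | 0.173 (0.122, 41%) | 0.252 (0.043, 15%) |

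In a repeat run, exit of 0% or 3% at confirmation gave a shortfall of about 0% or 2%. The table's shortfalls therefore come from the assumed exit rates. The simulation covers EDSS progression only. It has no relapses and no quality-of-life scores; SF-12 and EQ-5D are collected at Day 1 and Weeks 24, 48, 72 and 96, not at Week 84.

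**Step 3: ET scores in the Week 96 row.** Use the mixture with p = 10%, w = 40%, d = 15%, and let a fraction f of leavers attend ET, so that w and d become w(1−f) and d(1−f). Hold each leaver's change constant after ET. The Week 96 bias is −0.027 at f = 0, −0.012 at f = 50%, −0.005 at f = 80% and 0 at f = 100%. In a repeat simulation with 50% to 100% attendance, the Week 96 shortfall fell from 46–48% to 24–35% at 60% exit and from about 30% to 19–25% at 40% exit. It stayed near 15% at 20% exit. Pooling therefore softens the selection in that row, but it labels a score from an earlier week as Week 96.

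**The case against.** A reader might infer that Section 13.5 is an exit rule and that the means will be too favourable. The documents do not support that. The section asks for judgment and renewed consent, Protocol 7.2.1 keeps relapsing subjects eligible, and the mandatory reasons for stopping treatment in Protocol 8.1 name neither relapse nor progression. Without exit rates by event, the bias is possible, not shown.

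A reader might also infer that leavers vanish from every later row. That holds for the rows between exit and Week 96. At Week 96, the shared nominal visit means that ET scores may be included.

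Nor does the point extend to all efficacy results. The annualized relapse rate uses all relapses over patient-years, and the relapse proportion and confirmed progression use Kaplan-Meier (SAP 3.5.3). None is restricted to subjects still present, so events recorded before exit would be counted and could contradict a falsely flat EDSS curve.

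Finally, the endpoints are exploratory and descriptive in an open-label safety study, row counts are already planned, and the absolute bias is small against the 0.5-point EDSS step. All of this stands. It limits the weight of the point, but it does not supply the missing rule for ET scores or any check on drop-out.

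**Conclusion.** The concern holds in conditional form. By-visit EDSS, SF-12 and EQ-5D VAS means are open to a favourable bias if worsened subjects leave more often, and the plan has no analysis that would show or reduce it. The size is unknown. The illustrative 0.02 to 0.12 EDSS points at Week 84, or 13% to 43% of the change being estimated, rests wholly on an assumed 20% to 60% exit among confirmed progressors. It should not be read as an estimate for this trial, for relapse-driven exit or for quality of life.

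The unstated row for ET scores is a gap whatever the exit rate. No safety conclusion depends on either issue. Because a repeated-measures model still leaves part of the bias, it belongs beside the observed tables as a sensitivity analysis and not in their place.

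**What to change.** In SAP 3.5.3, 3.5.4 and 6.1:

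- Keep the observed tables.
- Assign each ET value, by actual study day, to the nearest scheduled visit for that endpoint, not to Week 96 by default. State which value is kept if that visit already has one.
- Add, as a prespecified sensitivity analysis, a likelihood-based repeated-measures model for EDSS, SF-12 PCS and MCS, and EQ-5D VAS, each at its own scheduled visits. Terms are baseline, visit, enrollment group and group-by-visit. Report mean change with 95% CI.
- Beside each observed row, show the baseline mean of the contributing subjects and the cumulative number who left after a relapse or progression.

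The ET rule and the model should be adopted together. Moving early ET scores out of the Week 96 row dates them correctly but gives up the partial correction in Step 3.

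The cost is SAP wording and one model per endpoint, with no new data or visits. The model assumes that missingness depends on recorded values, so it removes only part of any bias.
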